2.13 Crossover Phase

Baseline

Baseline is defined as the most recent non-missing value before the first dose of study treatment (dabrafenib plus trametinib) on the crossover treatment period. Baseline values will be established prior to the start of the crossover phase.

Response will be determined separately for the randomized phase and the crossover phase. Baseline lesion assessments will be re-established prior to initiation of crossover therapy and response will be calculated based on the appropriate baseline for each respective phase.

On-treatment assessment/event and observation periods

For AE reporting the overall observation period will be divided into three mutually exclusive segments:

- 1. *pre-treatment period*: up to 90 days prior to the first dose on the crossover phase
- 2. *on-treatment period*: from date of first administration of crossover study treatment to 30 days after date of last actual administration of study treatment (including start and stop date)
- 3. *post-treatment period*: starting at day 30+1 after last administration of crossover study treatment.

The reference date for both efficacy and safety measures in the Crossover phase is the date of first dose of dabrafenib or trametinib on the crossover treatment period.

The tables and listings for the randomized and crossover phases will be separate. Note: Analyses specified as for the Randomized phase will only include data prior to crossover except for analyses of OS. Similarly analyses specified for the crossover phase will only use data from after the date of crossover.

Only key summary tables will be provided for the crossover phase for example; disposition, treatment discontinuation, exposure, deaths, AE/SAEs, ORR, and time to response. Listings will be provided for the crossover data.

3 Sample size calculation

The sample size calculation was based on the primary analysis and is not applicable for the final analysis.

4 Change to protocol specified analyses

No change from protocol specified analysis was made.

5 Appendix

5.1 Imputation rules

5.1.1 Study drug

The following rule should be used for the imputation of date of last administration for a given study treatment component:

Scenario 1: If the date of last administration is completely missing and there is no EOT eCRF page and no death date, the patient is considered as on-going:

The patient should be treated as on-going and the cut-off date should be used as the last dosing date.

Scenario 2: If the date of last administration is completely or partially missing and the EOT eCRF page is available (prior to any death date or withdrawal of consent date, if available):

Case 1: The date of last administration is completely missing, and the EOT visit date is complete, then this latter date should be used.

Case 2: Only Year (yyyy) of the dose end date is available and yyyy < the year of EOT date:

Use Dec31yyyy

Case 3: Only Year(yyyy) of the dose end date is available and yyyy = the year of EOT date:

Use EoT date

Case 4: Both Year(yyyy) and Month (mm) are available for the date of last administration, and yyyy = the year of EOT date and mm < the month of EOT date:

Use last day of the Month (mm)

All other cases should be considered as a data issue and the statistician should contact the data manager of the study.

After imputation, compare the imputed date with start date of that specific record, if the imputed date is < start date of that record:

Use the start date of that record

Patients with missing start dates are to be considered missing for all study treatment component related calculations and no imputation will be made. If the date of first administration is missing, then the date of last administration should not be imputed.

5.1.2 AE, ConMeds and safety assessment date imputation

Table 5-1 Imputation of start dates (AE, CM) and assessments (LB, EG, VS)

Missing Element	Rule
day, month, and year	• No imputation will be done for completely missing dates
day, month	 If available year = year of study treatment start date then If stop date contains a full date and stop date is earlier than study treatment start date then set start date = 01JanYYYY Else set start date = study treatment start date. If available year > year of study treatment start date then 01JanYYYY If available year < year of study treatment start date then 01JulYYYY
day	 If available month and year = month and year of study treatment start date then If stop date contains a full date and stop date is earlier than study treatment start date then set start date= 01MONYYYY. Else set start date = study treatment start date. If available month and year > month and year of study treatment start date then 01MONYYYY If available month and year < month year of study treatment start date then 15MONYYYY

Table 5-2	Imputation of end dates	(AE, CM)
-----------	-------------------------	----------

Missing Element	Rule (*=last treatment date plus 30 days not > (death date, cut-off date,
	withdrawal of consent date))
day, month, and year	• Completely missing end dates (incl. ongoing events) will be imputed by the end date of the on-treatment period*
day, month	• If partial end date contains year only, set end date = earliest of 31DecYYYY or end date of the on-treatment period *
day	• If partial end date contains month and year, set end date = earliest of last day of the month or end date of the on-treatment period*

Any AEs and ConMeds with partial/missing dates will be displayed as such in the data listings.

Any AEs and ConMeds which are continuing as per data cut-off will be shown as 'ongoing' rather than the end date provided.

The above imputations are only used for analyses of time to and duration of AEs and concomitant medications, and for assigning pre/on/post treatment periods.

5.1.2.1 Other imputations

Incomplete date of antineoplastic medications, radiotherapy, surgery, initial diagnosis of cancer or date of most recent recurrence

Missing day is defaulted to the 15th of the month and missing month and day is defaulted to 01-Jan.

Incomplete assessment dates for tumor assessment

All investigation dates (e.g. MRI scan, CT scan) must be completed with day, month and year. If one or more assessment dates are incomplete but other investigation dates are available, this/these incomplete date(s) are not considered for calculation of the assessment date and assessment date is calculated as the latest of all investigation dates (e.g. MRI scan, CT scan) if the overall response at that assessment is CR/PR/SD/UNK. Otherwise – if overall response is progression – the assessment date is calculated as the earliest date of all investigation dates at that evaluation number. If all measurement dates have no day recorded, the 1st of the month is used. If the month is not completed, for any of the investigations, the respective assessment will be considered to be at the date which is exactly between previous and following assessment. If a previous and following assessment is not available, this assessment will not be used for any calculation.

Applying the cut-off to tumor assessment

For tumor related assessments, if an evaluation has some assessments done prior to cut-off date and others after the cut-off date, then the evaluation is considered post-cut-off date and will be excluded from analysis.

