If a patient receives any further anti-neoplastic therapy while on study, any subsequent assessments will be excluded from the BOR determination for the primary endpoint. Further anti-neoplastic therapies will be identified via protocol deviations or from the data collected on 'Anti-neoplastic therapies since last date of study drug' as appropriate.

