2.7.3 Handling of missing values/censoring/discontinuations

DOR and PFS

If a patient has not progressed or is not known to have died at the date of analysis cut-off or has received any further anticancer therapy, DOR and PFS will be censored at the date of the last adequate tumor before the cut-off date or before the start of the new anticancer therapy date, whichever is earlier.

The date of last adequate tumor assessment is the date of the last tumor assessment with overall lesion response of CR, PR or SD before an event or a censoring reason occurred. In this case the last tumor evaluation date at that assessment will be used. If no post-baseline assessments are available (before an event or a censoring reason occurred) then the date of randomization will be used.

In particular, DOR and PFS will be censored at the last adequate tumor assessment if one of the following occurs: absence of event; the event occurred after a new anticancer therapy is administered; the event occurred after two or more missing tumor assessments. The term "missing adequate tumor assessment" is defined as a tumor assessment (TA) not performed or tumor assessment with overall lesion response of "UNK". The rule to determine number of missing TAs is based on the time interval between the date of last adequate tumor assessment and the date of an event. If the interval is greater than twice the protocol-specified interval between the TAs and 2 times the protocol-allowed time window around assessments, then the number of missing assessments will be 2 or more.

Refer to Table 2-13 for censoring and event date options and outcomes for DOR and PFS.

Situation	Date	Outcome
No baseline assessment	Date of randomization	Censored
Progression or death at or before next scheduled Assessment	Date of progression (or death)	Progressed
Progression or death after exactly one missing assessment	Date of progression (or death)	Progressed
Progression or death after two or more missing assessments	Date of last adequate assessment prior to missed assessment	Censored
No progression (or death) New anticancer therapy (including cancer related surgery and radiotherapy) given prior to protocol defined progression (including patients	Date of last adequate assessment Date of last adequate assessment on or prior to starting new anti- cancer therapy	Censored Censored

Table 2-13Outcome and event/censor dates for DOR and PFS analysis

Novartis	Confidential	Page 38
SAP Final CSR LGG		CDRB436G2201

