5.6 Estimands

5.6.1 Primary estimand for the primary objective

The primary clinical question of interest is: what is the relative effect of the two treatment strategies in increasing the ORR by independent review as per RANO criteria in children and adolescent subjects with BRAFV600 mutant LGG with PD, regardless of study treatment discontinuation and before start of any new anti-neoplastic therapy.

The justification for the primary estimand is that it will capture the treatment effect of the study drug even after treatment is discontinued, but avoid potential confounding effects of any other new anti-neoplastic therapy.

The primary estimand is characterized by the following attributes:

- 1. Population: all subjects randomized with BRAFV600 mutant LGG with PD following surgical excision, or non-surgical candidates with necessity to begin first systemic treatment because of a risk of neurological impairment with progression. Further details on the population are provided in protocol Section 5.
- 2. Primary Variable: BOR by independent review as per RANO criteria.
- 3. Treatment: the randomized treatment (the investigational treatment dabrafenib plus trametinib or the control treatment vincristine plus carboplatin), regardless of treatment discontinuation.

Handling of intercurrent events:

- **Discontinuation of study treatment for any reason:** Per treatment policy strategy, tumor assessment data collected after discontinuation of study treatment for any reason will be used to derive BOR. This includes subjects who were randomized but not treated.
- Start of new anti-neoplastic therapy: Per while on treatment strategy, tumor assessments collected before start of new anti-neoplastic therapy will be used to derive BOR. Tumor assessments collected on/after the start of new therapy will not be considered for evaluation of BOR.

Summary measure: proportion of subjects with BOR of a confirmed CR or PR by independent review as per RANO criteria between the treatment arms as assessed by the Mantel-Haenszel chi-squared test. See sections 2.5.2 for details.

Sensitivity analyses for primary endpoint/estimand will be performed using the evaluable set, with all other aspects of the estimand as defined above. Additionally, analyses with response as assessed by the investigator (instead of by central review) will be done under the same estimand attributes.

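### LGG final SAP 5.1.2.1 imputes partial dates of anticancer therapy with no lower limit, so therapy given after progression can be dated before it, or before randomization

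*SAP*

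**What the plan says.** In the LGG final SAP, section 5.1.2.1, the relevant rule is headed "Incomplete date of antineoplastic medications, radiotherapy, surgery, initial diagnosis of cancer or date of most recent recurrence". Its text is "Missing day is defaulted to the 15th of the month and missing month and day is defaulted to 01-Jan". The heading is not restricted to prior therapy. Section 2.4.2 refers prior anticancer therapy back to the primary analysis, so the therapy dates that matter for efficacy in this SAP are those of on-study and post-treatment therapy.

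Those dates are used in three places:

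- **PFS and DOR (2.7.3).** Censoring applies if "the event occurred after a new anticancer therapy is administered". The censoring date is the last adequate assessment before the cut-off or "before the start of the new anticancer therapy date, whichever is earlier". If nothing is left: "If no post-baseline assessments are available (before an event or a censoring reason occurred) then the date of randomization will be used".
- **Best overall response (2.5.1).** After further antineoplastic therapy, "any subsequent assessments will be excluded from the BOR determination for the primary endpoint".
- **Primary estimand (5.6.1).** "Tumor assessments collected on/after the start of new therapy will not be considered for evaluation of BOR". Under 5.6.2 an unknown best response counts as non-response.

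The 2021 LGG SAP and the HGG final SAP apply the 15th/1 January default only to diagnosis and recurrence dates. The therapy dates were added in the LGG final SAP.

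**The concern.** For a diagnosis date, a mid-month or 1 January default does little harm. For the start of a new therapy it acts on the order of two events, and that order decides whether a progression is counted. The rule does not compare the imputed date with randomization, the last study dose or a documented progression.

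No other rule in the SAP corrects this. Table 5-1 in 5.1.2 does pull partial start dates up to the start of study treatment, but the text below the tables limits those imputations to adverse events, concomitant medications and the assignment of treatment periods.

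At stake are the main PFS and DOR estimates, the PFS hazard ratio, and ORR. A true event can become a censoring at an earlier scan, and a responder can lose the scans that established the response.

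**Working it through.** The plan gives no figure on this point to reproduce. The check applies the rule by date arithmetic.

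**Inputs.** From the SAP: the default values (5.1.2.1), the censoring and scan-exclusion rules (2.5.1, 2.7.3, 5.6.1) and a month length of 30.4375 days (2.1.1). Assumed: therapy starts *g* days after progression, and start days are spread evenly over the calendar (2021 to 2023, 365-day years). A reversal is counted only if the imputed therapy date falls strictly before the progression date.

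**Size of the date error.**
- Day missing: from 16 days early (true date the 31st) to 14 days late (true date the 1st).
- Day and month missing: up to 364 days early (365 in a leap year), never late.

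**Day missing.** If therapy starts on day *d* of a month with *L* days, progression is on day *d* − *g*. The order is reversed if *d* − *g* > 15, which gives max(0, *L* − 15 − *g*) days per month. A year has seven months of 31 days, four of 30 and one of 28.
- *g* = 3: (7×13 + 4×12 + 10)/365 = 149/365 = 41%
- *g* = 7: (7×9 + 4×8 + 6)/365 = 101/365 = 28%
- *g* = 14: (7×2 + 4×1 + 0)/365 = 18/365 = 5%
- *g* = 21 or more: 0%. The count already reaches zero at *g* = 16, since 31 − 15 − 16 = 0.

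**Day and month missing.** If therapy starts on day *D* of the year, the order is reversed if *D* − *g* > 1, which gives 364 − *g* days per year.
- *g* = 7: 357/365 = 98%
- *g* = 14: 350/365 = 96%
- *g* = 28: 336/365 = 92%
- *g* = 56: 308/365 = 84%

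**Example, day missing.** Progression on 18 March 2021, therapy on 25 March recorded as March 2021. The imputed start is 15 March. The progression now falls after new therapy and is censored at the previous adequate scan.

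**Example, year only.** Randomization on 2 March 2020, PR from week 16 (15 June) to week 32 (5 October), progression on 7 December 2020, therapy later that December recorded as 2020. True PFS is 281/30.4375 = 9.2 months, counting both end dates. The imputed start is 1 January 2020, before randomization. No post-baseline scan remains, so PFS is censored at randomization, and best response changes from PR to unknown, a non-responder. The visit dates are illustrative.

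**The case against.** Much of the case on the other side stands.

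- **Few records may be affected.** The SAP gives no count of partial dates. Section 1.1 says later therapies are collected at three-monthly survival contacts, which makes partial dates plausible but does not show them. Therapies first started in that phase will often follow progression by more than three weeks, where the day-missing rule causes no reversal.
- **Mitigation is planned.** The final analysis is descriptive (2.5.2, 2.7.2). Section 2.7.4 repeats PFS and DOR ignoring new therapy, and 2.5.4 does so for ORR if data permit. None of these depends on therapy dates. They do not, however, correct the main outputs.
- **The formal tests are not touched.** They belonged to the primary analysis under the 2021 SAP, whose default did not cover therapy dates.

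Some stronger readings are tempting but not supported:

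- *The arm with more progression is hit harder, so the hazard ratio is biased in a known direction.* Crossover counts as new therapy in Table 2-13, but it requires centrally confirmed progression and its start is the first non-zero dose (2.1.1), taken from dosing records. An unknown share of control patients is therefore outside the rule, and the direction cannot be stated.
- *Same-day ties are reversals too.* Counting them gives about 44%, 31% and 8% at 3, 7 and 14 days. Section 2.7.3 censors an event after new therapy, which a tie is not. Only the estimand's wording for scans reaches ties.
- *The SAP already makes such an order check for study drug.* Section 5.1.1 says "After imputation, compare the imputed date with start date of that specific record, if the imputed date is < start date of that record", but that is a check within one dosing record, not between events.
- *A missing day costs a confirming scan.* Where therapy follows progression, an error of at most 16 days does not reach back across an eight-week scan interval. The loss needs a year-only date, or therapy begun without progression, which is not quantified here.

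**Conclusion.** The concern holds as a defect in a stated rule. Followed as written, it can give impossible sequences, such as new therapy before randomization. The practical weight lies with year-only dates, where the error always runs early and reverses 92% to 98% of progression-then-therapy sequences at gaps of 28 down to 7 days. Day-only gaps matter when therapy follows progression within about two weeks.

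These shares rest on the assumed gaps and an even spread of dates, and apply only to records with a partial date. The effect on the PFS, DOR and ORR estimates cannot be sized from the SAP, and no between-arm direction can be claimed. It is worth correcting because the main outputs use the rule and the correction is small.

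**What to change.** In 5.1.2.1 of the LGG final SAP:

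1. Keep the 15th/1 January default for diagnosis, recurrence and prior therapy.
2. For therapy recorded since last study drug, set the imputed start no earlier than the day after the last study dose. For on-study therapy found through protocol deviations, set it no earlier than randomization. Keep the date within the known month or year and not after the therapy's end date.
3. Where a documented progression falls in the same known period, list the case and report PFS and DOR twice: with therapy dated after the progression, and with the default date. This step is needed because a patient may have stopped study treatment well before progressing, and the lower limit from the last dose then does not protect the order.
4. State the same rule in the HGG final SAP, which has none for these dates.

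The cost is one paragraph, a small change to the derivation and one listing. The downside is that a therapy truly started just before progression in the same period may be kept as an event; the listing shows these cases.

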5.2 AEs coding/grading

AEs are coded using the Medical dictionary for regulatory activities (MedDRA) terminology.

AEs will be assessed according to the CTCAE version 4.03.

The CTCAE represents a comprehensive grading system for reporting the acute and late effects of cancer treatments. CTCAE grading is by definition a 5-point scale generally corresponding to mild, moderate, severe, life threatening, and death. This grading system inherently places a value on the importance of an event, although there is not necessarily proportionality among grades (a grade 2 is not necessarily twice as bad as a grade 1).

5.3 Systemic corticosteroids

Systemic corticosteroids should be flagged based on a list provided by the clinical team. Further details will be provided in the programming datasets specifications (PDS).

The total daily dose can be calculated by multiplying the dose per administration by the factor specified in Table 5-3 according to the specified dosing frequency.

Tuble 0-0 multiplicative factors to calculate total daily (
Frequency	Meaning	Multiply dose per administration	
BID	Twice per day	2	
BIW	Twice per week	0.2857	
Continuous	-	Set to missing	
Daily	Once per day	1	
Once	-	1	
Other	-	Set to missing	
PRN	As required	Set to missing	
QD	Once per day	1	
QH	Once per hour	24	
Q2H	Once every 2 hours	12	
Q3H	Once every 3 hours	8	
Q4H	Once every 4 hours	6	
Q5H	Once every 5 hours	4.8	
Q6H	Once every 6 hours	4	
Q8H	Once every 8 hours	3	
Q12H	Once every 12 hours	2	
Q14H	Once every 14 hours	1.7143	
Q18H	Once every 18 hours	1.3333	
Q24H	Once every 24 hours	1	
QID	Four times per day	4	
QM	Once per month	0.0328	
Q2M	Once every 2 months	0.0164	
Q3M	Once every 3 months	0.0110	
QOD	Once every other day	0.5	
QW	Once per week	0.1429	
Q2W	Once every 2 weeks	0.0714	
Q3W	Once every 3 weeks	0.0476	
Q4W	Once every 4 weeks	0.0357	
TID	Three times per day	3	
TIW	Three times per week	0.4286	
Unknown	-	Set to missing	
Weekly	Once per week	0.1429	
5x per day	Five times per day	5	
6x per day	Six times per day	6	
7x per day	Seven times per day	7	
8x per day	Eight times per day	8	

Table 5-3	Multiplicative factors to calculate total daily dose
-----------	--

5.4 Laboratory parameters derivations

Grade categorization of lab values will be assigned programmatically as per NCI CTCAE version 4.03. The calculation of CTCAE grades will be based on the observed laboratory values only, clinical assessments will not be taken into account. The criteria to assign CTCAE grades are given in Novartis internal criteria for CTCAE grading of laboratory parameters. The latest available version of the document based on the underlying CTCAE version 4.03 at the time of analysis will be used.

For laboratory tests where grades are not defined by CTCAE v4.03, results will be graded by the low/normal/high (or other project-specific ranges, if more suitable) classifications based on laboratory normal ranges.

A severity grade of 0 will be assigned for all non-missing lab values not graded as 1 or higher. Grade 5 will not be used. For laboratory tests that are graded for both low and high values, summaries will be done separately and labelled by direction, e.g., sodium will be summarized as hyponatremia and hypernatremia.

Imputation Rules

CTC grading for blood differentials is based on absolute values. However, this data may not be reported as absolute counts but rather as percentage of white blood cells (WBC).

If laboratory values are provided as '<X' (i.e. below limit of detection) or '>X', prior to conversion of laboratory values to SI unit, these numeric values are set to X.

The following rules will be applied to derive the WBC differential counts when only percentages are available for a xxx differential

xxx count = (WBC count) * (xxx %value / 100)

Further derivation of laboratory parameters might be required for CTCAE grading. For instance, corrected calcium can be derived using the reported total calcium value and albumin at the same assessment using the following formula:

Corrected Calcium (mg/dL) = Calcium (mg/dL) - 0.8 [Albumin (g/dL)-4]

In order to apply the above formula, albumin values in g/L will be converted to g/dL by multiplying by 0.1), calcium values in mmol/L will be converted to mg/dL by dividing by 0.2495. For calculation of laboratory CTC grades 0 and 1, the normal range for derived corrected calcium is set to the same limits (in mg/dL) as for calcium.

CTC grades for the derived absolute WBC differential counts (neutrophils, lymphocytes) and corrected calcium will be assigned as described above for grading

